## **Study protocol and Statistical analysis plan**

**#NCT02707575**

### **Cytokeratin 8 level in Aqueous Humor, as a prognostic factor for visual and anatomical outcomes after Ranibizumab (Lucentis) in Neovascular Age-related Macular Degeneration**

**Date: December 4, 2020**

#### **1. Objectives:**

The cytokeratin 8 (CK8) level of aqueous humor in neovascular age-related macular degeneration (nAMD) patient is related to the visual and anatomical outcomes after Lucentis (Ranibizumab).

Primary objective To investigate the correlation between the CK8 level of aqueous humor in neovascular age-related macular degeneration (nAMD) patient and the best corrected visual acuity change after Lucentis

Secondary objectives To investigate the correlation between the CK8 level of aqueous humor in neovascular age-related macular degeneration (nAMD) patient and the retinal thickness change after Lucentis (Ranibizumab).

Explorative objectives: Associations of the baseline CK8 level with patients characteristics (with age, sex, type of new vessel (NV) and the OCT parameters including CNV size and central subfield macular thickness (CMT).

#### **2. Design**

non-randomized, open-label, Prospective observational study

#### **3. Method**

The prospective study was performed at the Severance Hospital, Gangnam Severance Hospital of Yonsei University and Isan Paik Hospital of Inje University between April 2016 and April 2018.

Procedures were in accordance with the Declaration of Helsinki and approved by the ethics committee of each institution. All study participants provided written informed consent.

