#### ***Study participants***

All patients were required to be least 50 years old with newly diagnosed (treatment-naïve) nAMD. The disease must be recent and confirmed via medical history and clinical findings. Patients were excluded if their eyes exhibited one of the following features: myopia with a refractive error greater than  $\pm 3.0$  diopters or evidence of pathologic myopia (preoperative refractive data were used to assess pseudophakic eyes); any history of vitrectomy, anti-VEGF therapy, laser treatment, or photodynamic therapy (PDT); history of cataract surgery within 3 months prior to presentation; evidence of end-stage AMD such as subfoveal fibrosis or atrophy; eyes with large submacular hemorrhage (SMH) over 1 disc-diameter; evidence of other retinal diseases including central serous chorioretinopathy, diabetic retinopathy, hypertensive retinopathy, or other neovascular maculopathies; glaucoma; poor imaging data due to media opacity; and unstable fixation. Patients with uncontrolled systemic diseases, use of immunosuppressive drugs, or malignant tumors at any location were also excluded. Controls were age- and sex-matched patients who underwent cataract surgery. Preoperative evaluation excluded individuals from the control group if they had eyes with ophthalmic diseases other than cataracts or eyes that met the exclusion criteria.

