### ***Statistical analysis***

Between-group differences in baseline characteristics and CK8 were determined with independent t tests (two-tailed) for continuous variables and Chi-squared tests for categorical variables. Pearson's correlations was used to evaluate the relationship between baseline CK8 and continuous baseline characteristics, while independent t tests were used to compare how baseline CK8 differed across

categorical baseline characteristics. A paired t-test compared CK8 before and after IVR, whereas another independent t-test compared CK8 between responders (dry nAMD eyes) and poor responders (persistent fluid). The association between CK8 and visual outcome was determined with linear regression, while the association between CK8 and anatomical outcome was determined with logistic regression. A multivariate regression was then performed, with the dependent variable being treatment outcome and independent variables being clinically significant parameters associated with treatment outcome in univariate analyses. All statistics were performed in SPSS for Windows (version 21.0; IBM Corp., Armonk, NY). Significance was set at  $p < 0.05$ .

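### Three hospitals contribute data but no planned analysis accounts for hospital, so hospital differences aligned in CK8 and outcome could create or mask a CK8-outcome association

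*Combined protocol and SAP*

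**What the plan says.** Section 2 describes a "non-randomized, open-label, Prospective observational study". Section 3 places it at three hospitals under two universities: "The prospective study was performed at the Severance Hospital, Gangnam Severance Hospital of Yonsei University and Isan Paik Hospital of Inje University". The primary objective, which concerns outcome following ranibizumab, reads: "To investigate the correlation between the CK8 level of aqueous humor in neovascular age-related macular degeneration (nAMD) patient and the best corrected visual acuity change".

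The Statistical analysis section is the whole analysis plan. For the main question it states: "The association between CK8 and visual outcome was determined with linear regression, while the association between CK8 and anatomical outcome was determined with logistic regression". It continues: "A multivariate regression was then performed, with the dependent variable being treatment outcome and independent variables being clinically significant parameters", the criterion being "independent variables being clinically significant parameters associated with treatment outcome in univariate analyses". No list of candidate covariates is given. Hospital appears in none of the t tests, chi-squared tests, correlations or regressions. That the data are pooled across hospitals is inferred from this silence; it is not stated in words.

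On the comparison group, the Study participants section says: "Controls were age- and sex-matched patients who underwent cataract surgery". It does not say at which hospital or hospitals controls were recruited.

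**The concern.** CK8 is a measured exposure in a non-randomized study, so nothing in the design balances it across hospitals. Aqueous samples are drawn and acuity is tested at the hospitals, so hospital can influence both ends of the association:

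- **CK8:** through case mix, and through storage. The freezer temperature is given, but not how long or where samples were stored, nor how they were batched for assay.
- **Outcome:** through case mix (the four neovascular subtypes may be referred differently), and through Snellen testing, for which no standardization across hospitals is described.

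If the hospital with higher CK8 also has worse or better outcomes, a pooled regression reads that between-hospital difference as a patient-level CK8 effect. If the hospital pattern runs against a true effect, pooling weakens it. The comparison of nAMD eyes with controls is open to a similar distortion if the ratio of cases to controls differs by hospital.

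**Working it through.** **Inputs from the documents.** Three hospitals (section 3); linear regression for the visual outcome and a threshold of 0.05 (Statistical analysis: "Significance was set at" that level). The documents give no sample size, SD, effect size or count per hospital, so there is no figure of the plan's own to reproduce.

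**Assumed inputs.** Hospital shares 40/35/25%; n = 60 or 100; within-hospital SD of 1 and within-hospital correlation of 0; hospital means shifted by -k, 0 and +k SD in both CK8 and outcome; two-sided test. The extreme hospitals are therefore 2k SD apart.

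**Step 1: spurious correlation.** The between-hospital variance of the shifts is

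(0.40 + 0.25)k² - (-0.40k + 0.25k)² = 0.65k² - 0.0225k² = 0.6275k².

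The shifts are identical in both variables, so this is also their covariance, and the pooled correlation is r = 0.6275k² / (1 + 0.6275k²).

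**Step 2: false-positive rate.** Approximately Φ(z - 1.96) + Φ(-z - 1.96), with z = atanh(r) × √(n - 3). The simulated column covers repeated runs of the exact regression test.

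| n | Extremes apart (2k) | r | z | Formula | Simulated, pooled |
|---|---|---|---|---|---|
| 60 | 0.5 SD | 0.038 | 0.285 | 5.9% | 5-6% |
| 60 | 1.0 SD | 0.136 | 1.030 | 17.8% | 17-18% |
| 60 | 1.5 SD | 0.261 | 2.016 | 52% | about 55% |
| 100 | 0.5 SD | 0.038 | 0.372 | 6.6% | 6-7% |
| 100 | 1.0 SD | 0.136 | 1.344 | 26.9% | 27-28% |
| 100 | 1.5 SD | 0.261 | 2.630 | 75% | 77% |

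With two hospital indicators added, the simulated rate is about 5% throughout.

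**Step 3: when there is no inflation.** If only one variable is shifted, the covariance of the shifts is zero, so r = 0. The same can happen when both are shifted but not aligned. With equal hospitals, CK8 shifts of 0, 0.5, 1 and outcome shifts of 0, 1, 0, the covariance is 0.5/3 - 0.5 × (1/3) = 0. Simulated rates for one-sided and non-aligned shifts lie between 4.6% and 6.0%.

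**Step 4: other shares and sizes.** With shares of one third each or 60/30/10%, and n from 40 to 120, aligned shifts give 5.2% to 7.4% with extremes 0.5 SD apart, and 9.4% to 35.2% with extremes 1 SD apart.

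**Step 5: masking.** Take a true within-hospital r of 0.35, n = 60, and shifts in opposite directions with k = 0.5. The pooled correlation falls to (0.35 - 0.1569) / 1.1569 = 0.167. Simulated power is 23% pooled and 78% with the hospital term.

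**Step 6: cost if hospitals do not differ.** At r = 0.35 and n = 60, atanh(0.35) = 0.3654.

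- Pooled: 0.3654 × √57 = 2.759, power about 78.8%.
- Adjusted, with two fewer degrees of freedom: 0.3654 × √55 = 2.710, power about 77.3%.

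Simulation gives 79.5% and 78.2%, a loss of about 1 point.

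**Step 7: acuity-testing offset.** Suppose hospital j adds a constant c_j to every acuity reading. Month 3 acuity carries c_j. Change carries (Month 3 + c_j) - (baseline + c_j), and c_j cancels. This route therefore affects the Month 3 outcome defined under Imaging and data analysis, but not the change named in the primary objective.

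**The case against.** The strongest reply is that the larger rates come from an unfavourable construction. They need hospitals far apart in both variables and in the same order, and nothing in the documents suggests differences of 1 SD or more. The documents also describe a good deal in common: one set of eligibility criteria, one injection protocol and sampling technique, named imaging devices, one ELISA kit with prompt freezing, and averaged readings by retinal specialists. This stands, and it makes large shifts less likely. It leaves storage time, assay batching, acuity testing and residual case mix unaddressed.

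A second reply is that the question is prognostic. If hospitals differ through real case mix, the unadjusted association is a legitimate quantity, and a hospital term removes its between-hospital part. This also stands, and is why both results should be shown.

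Third, forcing hospital into the logistic model may be unwise if few eyes have persistent fluid or one hospital is small. The event counts are unknown, so this stands too.

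Two stronger readings are tempting and not supported. A reader might infer that the covariate rule bars hospital from the multivariable model. It does not, because no candidate list is given; hospital is merely not named and not assured of entry. A reader might also infer that controls came from a different mix of hospitals than cases. The documents are silent on where controls were recruited, and the case-control contrast is not among the objectives in section 1.

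**Conclusion.** The omission is real: three hospitals, a non-randomized biomarker question, and no analysis that accounts for hospital. The consequence is conditional. It needs hospital differences in both CK8 and outcome that line up. Under the assumed shares and n = 60, inflation is negligible with extremes 0.5 SD apart, material at 1.0 SD (17-18%) and severe at 1.5 SD (about 55%). Sample size, shares and shifts are all assumptions.

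The documents do not support the conclusion that the CK8 result is biased, or that the highest rates are to be expected. No size can be put on the case-control comparison, because no control numbers or recruitment sites are given. The point is a low-priority improvement, worth making because the adjustment is cheap.

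**What to change.** 1. Add hospital as a fixed three-level factor (two indicators) to the linear regression of visual outcome and to its multivariable version, whatever its univariate p value. Show the unadjusted estimate beside it.
2. Add the same factor to the nAMD-versus-control comparison of CK8 if both groups were recruited at more than one hospital.
3. For the logistic model of persistent fluid, use hospital adjustment or stratification as a sensitivity analysis where event counts allow.
4. Report enrolment and baseline CK8 by hospital, and CK8 by assay batch, so that readers can judge whether shifts exist.

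The cost is SAP wording and a re-run. Hospital should already be known for every eye, so no new data are needed. The statistical price is two degrees of freedom, about 1 point of power in the linear model, and wider intervals in the logistic model if events are few.

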#### ***Study participants***

All patients were required to be least 50 years old with newly diagnosed (treatment-naïve) nAMD. The disease must be recent and confirmed via medical history and clinical findings. Patients were excluded if their eyes exhibited one of the following features: myopia with a refractive error greater than  $\pm 3.0$  diopters or evidence of pathologic myopia (preoperative refractive data were used to assess pseudophakic eyes); any history of vitrectomy, anti-VEGF therapy, laser treatment, or photodynamic therapy (PDT); history of cataract surgery within 3 months prior to presentation; evidence of end-stage AMD such as subfoveal fibrosis or atrophy; eyes with large submacular hemorrhage (SMH) over 1 disc-diameter; evidence of other retinal diseases including central serous chorioretinopathy, diabetic retinopathy, hypertensive retinopathy, or other neovascular maculopathies; glaucoma; poor imaging data due to media opacity; and unstable fixation. Patients with uncontrolled systemic diseases, use of immunosuppressive drugs, or malignant tumors at any location were also excluded. Controls were age- and sex-matched patients who underwent cataract surgery. Preoperative evaluation excluded individuals from the control group if they had eyes with ophthalmic diseases other than cataracts or eyes that met the exclusion criteria.

### ***Baseline evaluation, treatment, and AH sampling***

At baseline, each patient in the nAMD group underwent a comprehensive ophthalmological examination assessing best-corrected visual acuity (BCVA), intraocular pressure (IOP), autorefractometry/keratometry, slit-lamp biomicroscopy, indirect ophthalmoscopy, color fundus photography (FP), fluorescein angiography (FA), indocyanine green angiography (ICGA) (Optos® P200Tx, Optos PLC, Dunfermline, United Kingdom), and OCT (Swept source OCT DRI OCT Triton, Topcon, Tokyo, Japan). After baseline evaluation, nAMD patients were subjected to three consecutive intravitreal injections of 0.5 mg ranibizumab (Lucentis; Novartis, Basel, Switzerland) for 3 months, using a standardized protocol. Treatment outcome was monitored (BCVA, IOP, slit-lamp biomicroscopy, FP, and OCT) every time patients received an injection (baseline, Month 1, Month 2) and at 1 month after the third injection (Month 3). Along with injections, AH samples were taken at baseline, Month 1, and Month 2. Preoperatively, the eye was anesthetized topically using 0.5%

proparacaine hydrochloride. A 10% povidone-iodine scrub of lids and lashes was performed, and 5% povidone-iodine eye drops were applied to the ocular surface. The eye was draped in a sterile fashion, and a sterile lid speculum was inserted. A mean volume of 0.1 mL AH was collected via anterior chamber limbal paracentesis using a 30-gauge needle attached to an insulin syringe. Next, patients were given 0.5 mg IVR through the pars plana, 3–3.5 mm from the limbus. They were postoperatively treated with antibiotic eye drops (0.5% moxifloxacin hydrochloride) for 3 d.

Control subjects also underwent a comprehensive preoperative ophthalmological examination, including BCVA, IOP, ARK, slit-lamp biomicroscopy, indirect ophthalmoscopy, FP and OCT. Their AH samples were obtained immediately before cataract surgery.

---

#### ***Measurement of CYTOKERATIN 8 in AH***

Immediately after collection, AH samples were transferred to sterile plastic tubes (safe-lock microcentrifuge tubes, 1.5 mL), immediately frozen, and stored at -80°C until analysis. A sandwich enzyme-linked immunosorbent assay (ELISA) kit (Biomatik Corporation, Cambridge, Ontario) was used to quantitatively assess CK8 in AH. Samples were added to a 96 well microplate containing biotin-conjugated antibody specific to CK8. Avidin conjugated to horseradish peroxidase was added to each well, and the microplate was incubated. The addition of TMB substrate solution then generated a color change only in wells containing CK8 biotin-conjugated antibody and enzyme-conjugated avidin. After terminating the reaction with sulfuric acid solution, the color change was measured spectrophotometrically at a wavelength of 450 nm ± 10 nm. Sample CK8 concentration was then determined via comparing optical density of samples to the standard curve.

### ***Statistical analysis***

Between-group differences in baseline characteristics and CK8 were determined with independent t tests (two-tailed) for continuous variables and Chi-squared tests for categorical variables. Pearson's correlations was used to evaluate the relationship between baseline CK8 and continuous baseline characteristics, while independent t tests were used to compare how baseline CK8 differed across

categorical baseline characteristics. A paired t-test compared CK8 before and after IVR, whereas another independent t-test compared CK8 between responders (dry nAMD eyes) and poor responders (persistent fluid). The association between CK8 and visual outcome was determined with linear regression, while the association between CK8 and anatomical outcome was determined with logistic regression. A multivariate regression was then performed, with the dependent variable being treatment outcome and independent variables being clinically significant parameters associated with treatment outcome in univariate analyses. All statistics were performed in SPSS for Windows (version 21.0; IBM Corp., Armonk, NY). Significance was set at  $p < 0.05$ .

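### The nAMD–control CK8 comparison reads as an unadjusted t-test that ignores the age and sex matching; adjusting for both is a free improvement

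*Combined protocol and SAP*

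**What the plan says.** The Study participants section defines the comparison group: "Controls were age- and sex-matched patients who underwent cataract surgery". It does not say whether matching was by individual pairs or by group, and it gives no ratio, age tolerance or achieved balance.

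The Statistical analysis section says "Between-group differences in baseline characteristics and CK8 were determined with independent t tests (two-tailed) for continuous variables", with no covariate named. It does not define the groups. nAMD against control is the natural reading, because responders against poor responders get a separate t-test later in the section and no other CK8 analysis there would use the controls. The only paired test is CK8 before and after ranibizumab. The only multivariable model is described thus: "A multivariate regression was then performed, with the dependent variable being treatment outcome". Controls have no treatment outcome, so that model cannot cover the group contrast. The section also says that "independent t tests were used to compare how baseline CK8 differed across" categorical baseline characteristics, which describes associations with CK8 and does not adjust the group comparison.

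On the lens, the section on baseline evaluation and AH sampling has controls sampled just before their cataract operation, so with the natural lens in place. For nAMD eyes, Study participants excludes "history of cataract surgery within 3 months prior to presentation", which leaves earlier surgery admissible, and it notes that "preoperative refractive data were used to assess pseudophakic eyes". The exclusion for "poor imaging data due to media opacity" reaches both groups, since controls were excluded if they had "eyes with ophthalmic diseases other than cataracts or eyes that met the exclusion criteria". No adjustment or sensitivity analysis for lens status is named.

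**The concern.** Matching is done so that age and sex do not distort or blur the contrast, but an independent t-test uses neither variable. Two things could follow. If CK8 varies with age or sex, that variation stays in the error term and power is lost. If the matching was loose, any remaining imbalance passes straight into the estimated difference. The Objectives section itself treats age and sex as possible correlates of baseline CK8, since their association is an explorative objective.

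A second, lesser question is what a group difference would mean. All controls have a cataractous lens in place, while nAMD eyes may be pseudophakic, and age and sex matching does not remove that difference. If CK8 depended on lens state, some of an apparent nAMD effect could come from it.

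At stake is the interpretation of the one CK8 analysis that the plan implies for the controls.

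**Working it through.** The document gives no sample size, CK8 standard deviation, power or association of CK8 with age or sex, so there is no stated figure to reproduce. From the document: a two-sided test, significance at 0.05, independent t-test, age- and sex-matched controls. Assumed for illustration: 50 per group, and a share R² of CK8 variance explained by age and sex of 0, 10% or 30%.

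**Precision under exact balance.** The t-test's estimated SE exceeds the adjusted SE by 1/√(1−R²): 1/√1 = 1.000, 1/√0.9 = 1.054, 1/√0.7 = 1.195. If the adjusted analysis has 80% power, the true difference is 2.80 correct SEs, and the t-test needs 1.96/√(1−R²) of them:

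- R² = 0: Φ(2.80 − 1.96) = 80%
- R² = 10%: Φ(2.80 − 2.07) = 77%
- R² = 30%: Φ(2.80 − 2.34) = 68%

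Simulated SE ratios at 50 per group agree: 1.000, 1.054 and 1.194 with individual matching; 1.000, 1.054 and 1.197 with group-level matching. Adjusting therefore cost nothing where age and sex explained nothing.

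**Type I error of the t-test.** With exact balance it is 2[1 − Φ(1.96/√(1−R²))], which gives 3.9% at R² = 10% and 1.9% at 30%. That formula does not apply to looser matching. Simulation with one covariate and no group effect gave:

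| Matching achieved | t-test, R² 10% | t-test, R² 30% |
|---|---|---|
| Exact | 4.0% | 1.8% |
| Unpaired, same distribution | 4.9% | 5.1% |
| Unpaired, 0.2 SD residual imbalance | 6.1% | 8.1% |

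The linear model that included the covariate stayed near 5% in all of these. The last row can be checked by hand. An imbalance of 0.2 SD shifts the CK8 difference by 0.2√R² SD, that is 0.063 or 0.110. Dividing by √(2/50) = 0.2 gives 0.316 or 0.548. Then Φ(−1.96 + 0.316) + Φ(−1.96 − 0.316) = 6.2%, and with 0.548 it is 8.5%, close to the simulated values.

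**Lens status (illustration only).** Let s be the pseudophakic share of nAMD eyes. Let dP and dG be the CK8 differences, in SD, of pseudophakic and phakic nAMD eyes from the control lens state. The bias in the group difference is s·dP + (1−s)·dG, and the chance of p < 0.05 with no nAMD effect is Φ(−1.96 + b/√(2/n)) + Φ(−1.96 − b/√(2/n)).

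- s = 10%, dP = 0.2, dG = 0: b = 0.02; 5.1% at 50 per group, 5.2% at 100
- s = 30%, dP = 0.5, dG = 0: b = 0.15; 11.7% and 18.5%
- s = 30%, dP = 0.5, dG = −0.1: b = 0.15 − 0.07 = 0.08; 6.9% and 8.7%

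Restricting to phakic nAMD eyes leaves a bias of dG. That is 0 in the first two cases, but −0.10 in the third, which is larger in size than the 0.08 it replaces.

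**The case against.** The strongest reply is that an independent t-test is an acceptable analysis, that nothing in the document links CK8 to age or sex, and that adjustment gains nothing if there is no link. This stands as a limit on the size of the point. It does not remove it: the adjustment costs essentially nothing when R² is zero and helps whenever it is not.

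Two stronger readings are tempting on the matching. A reader might infer that ignoring it makes the test invalid; with exact balance it does the opposite and makes the test conservative. A reader might equally infer that the t-test is therefore safely conservative, or that the loss is sure to be small. The document supports neither, because it gives no matching type, tolerance, achieved balance or R². Only the conditional statement can be defended.

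On the lens, a reader might infer that the comparison is confounded. The eligibility and sampling rules create the asymmetry, but no text shows that CK8 depends on lens status or how many nAMD eyes were pseudophakic. The media-opacity exclusion limits dense cataract in both groups without equalising severity. The phakic-only remedy may also fail to reduce bias. These objections stand, so the lens element is optional.

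It can also be said that the study ran from April 2016 to April 2018, that the document is dated December 2020 and that its analysis is written in the past tense. That is correct, and the proposal is therefore a reanalysis.

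**Conclusion.** The point holds at low severity and rests on the age and sex adjustment. On the natural reading, the nAMD–control CK8 contrast uses neither matching variable. The power cost under exact balance is 0, 3 or 12 percentage points for R² of 0, 10% or 30%. The error rate may lie below, at or above 5% depending on the closeness of matching, which is unreported. All R² values, group sizes and imbalances are assumptions.

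The lens asymmetry supports only a caution against attributing a group difference to nAMD; the direction and size of any bias are unknown. A reader should not carry either element over to the primary or secondary results. Those concern CK8 within nAMD patients, and the control comparison appears in no listed objective.

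**What to change.** Replace the group t-test for CK8 with a linear model of CK8 on group, age and sex, and report the adjusted difference with its 95% CI. State whether matching was individual or by group and show the achieved balance. Add a matched-pair effect only if pairs were individual and recorded; no text mentions a recorded pair link. This is a reanalysis of collected data and should be labelled as such. Age and sex are already held, so it needs one model and a sentence of text.

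Optionally, report lens status in the nAMD group and repeat the model in phakic nAMD eyes against all controls, comparing estimates and 95% CIs rather than p-values. Lens status should be retrievable, because the refractive criterion requires pseudophakic eyes to be identified and both groups had slit-lamp examination. With equal group sizes, excluding a share s of nAMD eyes raises the SE by √((1/(1−s) + 1)/2): 1.03 times at 10% and 1.10 times at 30%. Agreement between the two estimates would not settle attribution, so keep the cautious wording either way.
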